2. INTRODUCTION

This is a phase II clinical study to explore and assess the efficacy and safety of SHR-1210 in treatment of hepatocellular carcinoma (HCC).

2.1. Study Design

This is a randomized, open-label, multi-center, phase II study. The primary objective is to evaluate the efficacy and safety of SHR-1210 in subjects with advanced HCC after failure of previous systemic treatment. A total of 220 subjects will be enrolled and randomized in a 1:1 ratio to receive SHR-1210 3 mg/kg, I.V., Q2W (once every two weeks) or SHR-1210 3 mg/kg, I.V., Q3W (once every three weeks) group, in 42-day cycles.

The study design schematic is presented in the following figure:

2.2. Study Objectives

To evaluate the efficacy and safety of anti-PD-1 antibody SHR-1210 in subjects with advanced hepatocellular carcinoma (HCC) who have received previous systemic treatment.

2.3. Sample Size

Referring to the study results on similar products, assuming the ORR is 15% for SHR-1210 in treatment of target population of this study, and the lower limit of 95% confidential interval of ORR obtained from this study is >7%, it can be considered as effective. 154 subjects need to be enrolled to obtain 90% power at a one-sided significance level of 0.025. Further assuming evaluable cases accounting for 80% of the enrolled subjects, 194 subjects are required to be enrolled.

Assuming the survival rate at 6 months is 80% for SHR-1210 in treatment of target population, and the lower limit of 95% confidential interval is >70%, this therapy can be considered to have advantage in efficacy. 200 subjects need to be enrolled to obtain 90% power at a one-sided significance level of 0.025. Considering the drop-out rate of 10%, a total of 220 subjects are required to be enrolled.

Considering the above two points, a total of 220 subjects will be enrolled in the study.

3. STATISTICAL HYPOTHESIS

All analyses will be primarily based on descriptive statistical summary by group and overall. No formal statistical hypothesis testing will be performed. The overall 95% CIs of the two primary study endpoints, ORR and 6-month OS rate, will be calculated. The lower limit of the overall 95% CI of ORR is > 7% and the lower limit of the overall 95% CI of 6-month OS rate is >70% indicate that the drug is effective.

4. STUDY ENDPOINTS

4.1. Efficacy Endpoints

4.1.1. Objective response rate (ORR)

Defined as the percentage of subjects with confirmed complete response or partial response (CR or PR) from the first dose of the investigational drug to PD assessed using RECIST 1.1 or start of new anti-cancer therapy.

4.1.2. Duration of response (DoR)

Defined as the period from the first documentation of CR or PR to the first documentation of PD or to death due to any reason in subjects with confirmed CR or PR. If no PD or death occurs, it will be censored at the last tumor assessment.

4.1.3. Disease control rate (DCR)

Defined as the percentage of subjects with CR, PR or stable disease (SD) for ≥ 6 weeks. A subject with missing or unknown evaluations is deemed not evaluable (NE). This subject will be included in the denominator to calculate percentage.

4.1.4. Progression-free survival (PFS)

Defined as the period from the date of first dose to the first documentation of PD in accordance with RECIST 1.1 or death due to any reason, whichever comes first. If a subject still shows no PD or does not die at the end of study, this period will be censored. The rules for PFS censoring are as below:

- If there is no tumor assessment at baseline, the date of censoring is the date of the first dose of study treatment.
- If there is no tumor assessment after baseline, the date of censoring is the date of the first dose of study treatment.
- If no RECIST 1.1 progression or death is recorded, the date of censoring is the date of the last tumor assessment.
- If no radiological progression or death is recorded prior to initiation of subsequent therapy, the date of censoring is the date of the last tumor assessment prior to the subsequent therapy.
- If subjects miss 2 or more consecutive planned tumor assessments prior to progression or death (12 weeks within 12 months from the first dose of study treatment, 24 weeks after 12 months from taking first dose), the date of censoring will be the date of the last tumor assessment.

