5. STATISTICAL ANALYSIS

5.1. General Considerations

5.1.1. Analysis sets

Full analysis set (FAS)

Full analysis set includes all the randomized subjects who have received at least one dose of the investigational drug. Based on the analysis in the FAS, subjects belong to their allocated group as randomized rather than the actual medication group.

Per-protocol set (PPS)

It is a subset of the FAS. The PPS forms by excluding subjects with protocol deviation that has important effect on the study results from the FAS. Analysis based on the PPS, as supportive analysis, will be used as a supplement to the analysis based on the FAS. The PPS must be determined by the medical team and the statistical team of the project prior to database lock for the final analysis. All protocol deviations, including those that are judged to have major effect on the study results, will be presented in study report in a form of listing.

Evaluable set (ES)

Evaluable set is also a subset of the FAS and defined as the subjects with at least one post-baseline tumor evaluation in the FAS.

Safety set (SS)

Safety set includes all the subjects who have received at least one dose of the investigational drug. Based on the analysis in SS, subjects belong to the actual medication group (as treated). The safety set is the primary set for the safety analyses.

PD-L1 set (PD-L1)

PD-L1 set of this study comprises of all subjects who have been randomized and have received at least one dose of the investigational drug, and have provided tumor biopsy samples.

Table 1. Correspondence between study endpoints and analysis sets

Endpoints	Analysis Sets				
	FAS	PPS	ES	SS	PD-L1
ORR (%)	X	X	X		X
6/9/12-month OS rate (%)	X	X			X
TTP (months)	X				
PFS (months)	X				
DoR (months)	X				
DCR (%)	X	X	X		
OS (months)	X				
TTR (months)	X				
Safety (AE, LAB, VS, ECG, PE)				X	

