5.4. Efficacy Analysis

The efficacy analysis will be performed separately by group and overall.

Efficacy analysis will be based on IRC-assessed data and investigator-assessed data, with the former as the primary analysis.

Based on the FAS, PPS, and ES, ORR and 95% CI will be calculated separately by group and overall. The CI will be calculated using the Clopper-Pearson method. In addition, the difference in ORR will be calculated between the two groups, and Wald method will be used to estimate the 95% CI of the difference, and the nominal P value will be calculated based on Pearson Chi-square test.

In addition, based on the FAS, Amit method will be used to analyze the discrepancy between IRC-assessed and investigator-assessed PD/non-PD, BOR, and CR/PR.

Based on the FAS and PPS, Kaplan-Meier method will be used to calculate the 6/9/12-month OS% and the corresponding 95% CIs will be calculated.

Based on the FAS, the secondary efficacy endpoint PFS (including the 6/9/12-month PFS rate), TTP, OS, and DoR will be analyzed using Kaplan-Meier method. TTR will be descriptively summarized. When applicable, the survival curve will be plotted by endpoints. For PFS, TTP, OS, and DoR, the hazard ratios between groups and their 95% CIs will be computed using the COX proportional hazards model and nominal P values will be calculated using the log-rank test.

For the secondary efficacy endpoint DCR, the same statistical method with ORR will be used for analysis based on the FAS, the PPS, and the ES.

The best overall response (BOR) will be summarized.

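### The SAP's PFS rule for subjects with no post-baseline scan censors at first dose without excepting deaths; coded literally, it modestly overstates PFS

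*SAP*

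**What the plan says.** SAP 4.1.4 measures PFS from first dose "to the first documentation of PD in accordance with RECIST 1.1 or death due to any reason, whichever comes first". Protocol 8.2 also counts death as a PFS event and gives no censoring rules. Before its list of rules the SAP says: "If a subject still shows no PD or does not die at the end of study, this period will be censored". Five bullets follow. The second is the one at issue: "If there is no tumor assessment after baseline, the date of censoring is the date of the first dose of study treatment". The first treats a missing baseline assessment in the same way. The fifth begins "If subjects miss 2 or more consecutive planned tumor assessments prior to progression or death (12 weeks within 12 months from the first dose" and censors at the last tumor assessment.

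PFS is analysed on the FAS (SAP 5.4, Table 1 in 5.1.1), and "Full analysis set includes all the randomized subjects who have received at least one dose of the investigational drug". No scan is needed to belong to it. SAP 5.4 states that "the secondary efficacy endpoint PFS (including the 6/9/12-month PFS rate), TTP, OS, and DoR will be analyzed using Kaplan-Meier method". The first post-baseline scan is due at week 8 ± 7 days, then every 6 weeks in the first year (protocol 3.2.2).

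**The concern.** A subject who is dosed and dies before any post-baseline scan has had a PFS event by definition, yet also meets the second bullet as written. If the bullet is coded literally, the death disappears and the subject leaves every later risk set. Subjects are then censored because they died early, so the censoring is informative and PFS can only move upward.

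Two programmers could code the rule differently, and the SAP gives them no ranking between a recorded death and this bullet. The 6/9/12-month PFS rates, the PFS curve and the between-group PFS hazard ratios all use the same derived times. The PFS analyses in sub-populations A to E may use them too. The revision table in SAP 1 says those sub-populations were added for comparison with other drugs, and there a censoring artefact would matter more.

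**Working it through.** **1. The five PFS bullets side by side (SAP 4.1.4)**

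| Bullet | Situation | Mentions death? | Censoring date |
|---|---|---|---|
| 1 | No baseline assessment | No | First dose |
| 2 | No post-baseline assessment | No | First dose |
| 3 | No progression or death | Yes, as a condition | Last assessment |
| 4 | New therapy with no earlier progression or death | Yes, as a condition | Last assessment before new therapy |
| 5 | Two or more missed assessments before progression or death | Yes, as an event set aside | Last assessment |

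Bullet 5 censors subjects who go on to progress or die, and bullet 4 reaches a subject who dies after starting new therapy. So the list is not confined to event-free subjects. Bullets 1 and 2 stand in identical words in the TTP list (SAP 4.1.5), where censoring a death fits the endpoint.

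**2. Inputs.** From the documents: N = 220, planned 6-month OS 80%, threshold 70% (SAP 2.3 and 3); first scan at week 8, day 56 (protocol 3.2.2). Assumed: constant death hazard, 6 months = 182.625 days, true 6-month PFS of 15% to 30%, and the share of early deaths that were scanned. The documents give no expected PFS.

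**3. The plan's own figure.** For 80% versus 70%, one-sided 0.025 and 90% power: n = (1.96√(0.7×0.3) + 1.2816√(0.8×0.2))² / 0.10² = 199.04, rounded up to 200. This matches the SAP, and 200 × 1.1 = 220. The 80% input is therefore used as the plan means it.

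**4. Deaths before week 8.** q = 1 − S6^(56/182.625).
- S6 = 0.80: q = 0.0661, or 14.5 of 220.
- S6 = 0.70: q = 0.1036, or 22.8 of 220.

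**5. Effect on Kaplan-Meier PFS.** After week 8 the number still event-free is the same under both codings, but the literal coding removes the unscanned deaths from the denominator. PFS is multiplied by 1/(1 − q), or by 1/(1 − q/2) if half had been scanned. The change in points is p × (factor − 1).

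| 6-month OS | Early deaths scanned | Factor | p = 15% | p = 30% |
|---|---|---|---|---|
| 80% | none | 1.071 | +1.1 | +2.1 |
| 80% | half | 1.034 | +0.5 | +1.0 |
| 70% | none | 1.116 | +1.7 | +3.5 |
| 70% | half | 1.055 | +0.8 | +1.6 |

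**6. Simulation on the protocol's scan schedule** (none scanned, ± 7-day jitter, assumed underlying median PFS of 2 and 3 months). At 80% OS, 6-month PFS moves from 15.3% to 16.4% and from 28.3% to 30.3%. At 70% OS it moves from 15.2% to 16.9% and from 27.9% to 31.1%. These agree with the factors above.

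**7. Scale.** The binomial SD of a rate in 220 subjects, √(p(1 − p)/220), is 2.4 points at 15% and 3.1 points at 30%. At 80% OS the bias is below one SD.

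**8. Later deaths.** Between days 56 and 84 a further 220 × (S6^(56/182.625) − S6^(84/182.625)) = 6.9 deaths (80%) or 10.5 (70%) are expected. They add to q only if the week-8 scan was also missed.

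**The case against.** The best defence is that the section already counts these deaths. The definition comes first, and the lead-in confines censoring to subjects without progression or death. Bullet 2 can then be read as merely supplying a date for someone already censored. Bullet 5 names the event it sets aside, which bullet 2 does not. The TTP list has a separate bullet that censors deaths, and its absence from the PFS list suggests that PFS deaths were meant to count. All of this stands as evidence of intent, and a programmer who follows the definition would get it right. It does not settle the text: if the lead-in governed the whole list, bullet 5 could not operate and the condition in bullet 3 would be redundant.

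The DoR rule in SAP 4.1.2 does state the condition ("If no PD or death occurs, it will be censored at the last tumor assessment"), but this is weak support for the concern, because a confirmed responder always has a post-baseline scan.

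The objection to size is also sound in part. The 70% case is the threshold to be exceeded, not the planning value. The scanned shares are assumptions. Entry requires a life expectancy of at least 12 weeks (protocol 5.1), which sits badly with a constant hazard from day 1. The protocol's follow-up schedule lists imaging at End-of-Treatment, so a subject who stops before week 8 may still be scanned. The figures are therefore ceilings for deaths before week 8.

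**Conclusion.** Wrong as written, but minor. Bullets 1 and 2 lack a death exception that the PFS definition needs. Under the literal reading the direction is certain: PFS is overstated. At the planned 80% 6-month OS the ceiling is about 7% relative, or about 1 to 2 points on an assumed 6-month PFS of 15% to 30%, and 0.5 to 1 point if half of the early deaths were scanned. At the 70% threshold the ceiling is about 11.6% relative. All of this rests on a constant hazard and the assumed PFS range.

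A reader might infer three stronger things that the documents do not support.
- That the SAP has decided to discard these deaths. The definition and lead-in favour counting them.
- That the effectiveness conclusion is at risk. PFS is secondary, SAP 3 says "No formal statistical hypothesis testing will be performed", and ORR, the 6-month OS rate and the two effectiveness criteria do not use this rule.
- That the 80% evaluable share in the sample-size text implies a 25% inflation (1/0.8). Nothing says that the other 20% are deaths without a scan.

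**What to change.** In SAP 4.1.4, add to bullets 1 and 2 the condition that no death is recorded. A death with no post-baseline assessment is then a PFS event on the date of death.

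Add one sentence on precedence:
- Bullets 4 (subsequent therapy) and 5 (two or more consecutive missed planned assessments) still take precedence over such a death.
- For a subject never scanned after baseline, bullet 5 applies only once two planned scans have been missed, at weeks 8 and 14 under protocol 3.2.2. A flat 12 weeks from first dose would censor a week-13 death at day 1 after only one missed planned scan.
- Where bullet 4 or 5 applies to such a subject, the censoring date is the date of first dose. This must be stated, because the last tumor assessment would be the baseline scan.

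Leave the TTP bullets unchanged. The cost is one clause, one sentence and one programming condition. Compared with literal coding, reported PFS becomes slightly less favourable.

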3.2.2 Treatment period

The treatment period starts from randomization, and the investigational drug must be given within 3 days after randomization.

A cycle is defined as 6 weeks. SHR-1210 3 mg/kg will be given i.v. drip over half an hour, no less than 20 minutes and no more than 60 minutes, including rinsing period, on D1, D15 and D29 of each cycle in Group A, and on D1 and D22 of each cycle in Group B. Physical examination and laboratory examinations will be conducted during treatment, AE and concomitant medications information will be collected.

The following evaluation will be completed within 72 hours prior to each administration of investigational drug in each cycle of therapy:

ECOG PS, physical examination (at least including heart, lungs, abdomen, skin), vital signs, hematology, urinalysis, blood biochemistry, and blood electrolytes examination. The investigational drug can be given only after investigators have reviewed the laboratory test results.

Since the second treatment cycles, the following assessment will be completed at D1 of each cycle:

Coagulation function, alpha fetoprotein, thyroid function (TSH, FT3, FT4), virology (HBV markers or HCV markers), and Child-Pugh class.

In accordance with RECIST v1.1, the initial tumor imaging evaluation is assessed at 8 weeks (± 7 days), and then every 6 weeks (± 7 days), with or without dosing. After 12 months of dosing (i.e., the first dose), if tumor assessment is still required, it should be performed every 12 weeks (± 14 days) until the disease progresses or end of the study (whichever happens later).

The subjects who are evaluated as progressive disease can continue to receive treatment if they meet the criteria defined in Section 3.2.4.

The treatment period will end and proceed to follow-up period when the subjects terminate the study (see Section 5.5).

Note: the specific study procedures during the treatment period are shown in the study flowcharts.

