4.1.5. Time to progression (TTP)

Defined as the period from first dose to PD. Rules for TTP censoring are as follows:

- If there is no tumor assessment at baseline, the date of censoring is the date of the first dose of study treatment.
- If there is no tumor assessment after baseline, the date of censoring is the date of the first dose of study treatment.
- If no RECIST 1.1 progression or death is recorded, the date of censoring is the date of the last tumor assessment.
- If subjects die before the onset of disease progression, the date of censoring will be the date of the last tumor assessment.

- If no radiological progression or death is recorded prior to initiation of subsequent therapy, the date of censoring is the date of the last tumor assessment prior to the subsequent therapy.
- If subjects miss 2 or more consecutive planned tumor assessments prior to progression or death (12 weeks within 12 months from the first dose of study treatment, 24 weeks after 12 months from the first dose of study treatment), the date of censoring will be the date of the last tumor assessment.

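### The missed-scan censoring rule for PFS and TTP equates two missed scans with 12 and 24 weeks, which for scan-detected progression are the gaps after one missed scan, and its censoring date is not tied to the start of the gap.

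*SAP*

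**What the plan says.** The PFS censoring list in SAP 4.1.4 opens its last bullet with "If subjects miss 2 or more consecutive planned tumor assessments prior to progression or death". It explains the count in brackets as "12 weeks within 12 months from the first dose of study treatment, 24 weeks after 12 months from taking first dose" and then states that "the date of censoring will be the date of the last tumor assessment". SAP 4.1.5 repeats the rule for TTP, with "12 weeks within 12 months from the first dose of study treatment, 24 weeks after 12 months from the first dose of study treatment". TTP is "Defined as the period from first dose to PD", so death is not a TTP event.

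The subsequent-therapy bullet in the same PFS list does tie its date to an event: "the date of censoring is the date of the last tumor assessment prior to the subsequent therapy".

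Protocol 3.2.2 sets the schedule: "the initial tumor imaging evaluation is assessed at 8 weeks" (7 days either side), "and then every 6 weeks (± 7 days), with or without dosing", and every 12 weeks (14 days either side) once 12 months have passed since the first dose.

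SAP 5.4 uses PFS and TTP for Kaplan-Meier estimates, hazard ratios between the two dosing groups and nominal log-rank P values, and PFS also for 6/9/12-month rates. SAP 3 says no formal hypothesis testing is done.

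**The concern.** The rule carries two triggers that disagree when the event is progression seen on a scan. The words require two missed scans. The weeks are reached after one. A programmer who codes a gap in days will censor progressions that the words keep, and which subjects are hit will depend on where their scans fell inside the visit window.

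The second problem is the censoring date. Such a rule is meant to stop the clock before the unobserved period. As worded, the last assessment can be taken to be the scan after the gap, so the unobserved weeks would count as progression-free time.

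At stake are the PFS and TTP curves, medians, landmark PFS rates and between-group hazard ratios.

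**Working it through.** **Inputs.** First scan at week 8, then an interval of 6 weeks (window 1 week either side) to month 12, then 12 weeks (window 2 weeks either side): Protocol 3.2.2. Trigger of two missed scans, glossed as 12 and 24 weeks: SAP 4.1.4 and 4.1.5.

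**The plan's own figures.** They reproduce as 2 × interval without windows: 2 × 6 = 12 and 2 × 12 = 24.

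**Gap to progression found on a scan.** After m missed scans, gap = (m + 1) × interval, plus or minus one window at each end.

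- One missed, 6-weekly: 2 × 6 = 12 weeks, range 10-14.
- Two missed, 6-weekly: 3 × 6 = 18 weeks, range 16-20.
- One missed, 12-weekly: 2 × 12 = 24 weeks, range 20-28.
- Two missed, 12-weekly: 3 × 12 = 36 weeks, range 32-40.

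Within the regular intervals, only a cut-off between 14 and 16 weeks (early) or 28 and 32 weeks (late) would separate one miss from two.

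**First interval.** With only week 8 missed and progression at week 14, the gap from first dose is 14 weeks, range 13-15. It always exceeds 12.

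**Deaths.** From the last scan to the close of the second missed window is 12-14 weeks (6-weekly) or 24-28 weeks (12-weekly). Here the gloss roughly works.

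**How often one miss passes the limit.** Assume scan days uniform and independent over the 15 possible days of a 6-weekly window. The chance that two deviations are equal is 1/15, so P(gap > 84 days) = (1 - 1/15)/2 = 7/15 = 47%, and P(gap ≥ 84 days) = 8/15 = 53%. For 12-weekly scans (29 days) the values are 14/29 and 15/29. If every scan falls on its nominal day they become 0% (>) and 100% (≥).

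**Events affected per 220 subjects.** The simulation used 150,000 subjects scaled to 220, exponential time to progression and scans at weeks 8 to 50 six-weekly, then 62, 74 and 86. Each scan was missed independently. The limit was 84 days if progression was found by day 365, otherwise 168. True medians ran from 2.7 to 5.5 months, the span of PFS medians quoted for targeted drugs in Protocol 1.2.1. The documents give no missed-scan rate, so 5%, 10% and 20% are assumptions.

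Extra progressions censored by the weeks compared with the count:

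| Setting | 5% | 10% | 20% |
|---|---|---|---|
| >, uniform scan days, no deaths or dropout | 9-11 | 17-20 | 28-34 |
| >, uniform scan days, with deaths and dropout | about 7 | 12-14 | 20-23 |
| >, nominal days, no deaths or dropout | 4-6 | 7-11 | 12-20 |
| >, nominal days, with deaths and dropout | 3-4 | 5-8 | 8-14 |
| ≥, nominal days, no deaths or dropout | 15-16 | 27-29 | 44-48 |

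Deaths and dropout means 10% dropout by month 6 (the 10% is from Protocol 11.1; its timing is assumed) and death without progression as 20% of the event hazard (assumed).

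**Censoring date.** Take scan at week 8, weeks 14 and 20 missed, progression at week 26. Censoring before the gap gives week 8. The literal text permits week 26, which is 26 - 8 = 18 weeks more. If the count governs, the subjects open to this are those whose progression follows two or more misses: about 1, 4 or 16 per 220 without deaths or dropout, and about 1, 2-3 or 9-11 with them.

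**The case against.** The sentence makes the count the condition and puts the weeks in brackets as a loose 2 × interval. It names no start and end for the gap and no operator. A programmer who follows the sentence counts scans, and no progression after a single miss is lost. This stands, and it makes the effect conditional. It does not settle the matter: the SAP never says that the count governs, and under that reading the bracket does no work.

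The date wording can fairly be read by its purpose, since censoring at a scan after the gap defeats the rule. For a death after missed scans, the last assessment already precedes the gap. That also stands; the point is one of clarification.

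The event counts rest on assumptions, and the settings without deaths or dropout are generous for previously treated advanced disease. The ranges therefore have to include the low setting.

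A reader might go further and infer from the follow-up table in the protocol's Study Procedures, which gives 6-weekly scans for subjects off study without progression, that two misses after month 12 span only 18 weeks and never reach 24. The documents do not support this. Protocol 3.2.3 keeps such subjects on the same frequency as before and the end of 3.2.4 on the original one, which under 3.2.2 points to 12-weekly scans after month 12. Those places need reconciling.

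A reader might also treat the different week figure in the SAP's revision table as an error. It is a change log, and nothing here rests on it.

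**Conclusion.** The point holds as an internal contradiction in a stated rule. For scan-detected progression, 12 and 24 weeks mark one missed scan, not two. The gloss roughly suits deaths in PFS and suits no TTP event.

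The size depends on what is programmed. With the count it is none. With the weeks and a strict inequality it is roughly 3-11, 5-20 or 8-34 extra censored progressions per 220 at assumed missed-scan rates of 5%, 10% or 20%, depending on scan timing, deaths and dropout. An at-least rule with scans on nominal days gives more. Progression at week 14 after missing only week 8 is censored in every case under the weeks. The unanchored date separately touches about 1, 2-4 or 9-16 subjects.

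In the simulations both problems moved the PFS/TTP median upward or not at all. No single shift is quoted, because the Kaplan-Meier median sits on scan dates and the result depends on where 50% falls.

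A reader might infer that the trial's efficacy conclusion is in doubt. It is not: PFS and TTP are secondary and descriptive, and ORR, 6-month OS and the sample size do not use this rule. It should still be corrected, because it can give a wrong secondary result and is cheap to repair.

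**What to change.** In SAP 4.1.4 and 4.1.5:

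- Delete the bracketed 12- and 24-week figures.
- State that the count of consecutive missed planned assessments governs, where missed means that the window closed with no adequate scan, under the protocol schedule that applies to the subject at that time.
- Set the censoring date to the last adequate tumor assessment before the missed assessments, or first dose if there is none after baseline.

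Separately, reconcile the protocol's statements on scan frequency after month 12 for subjects off treatment without progression (Study Procedures follow-up table, 3.2.2, 3.2.3 and the end of 3.2.4). The SAP rule should refer to the applicable schedule and not choose among them.

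The cost is SAP wording and one derivation. The downside is that reported PFS and TTP may be shorter than under the week limits.
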